3.4 Tools and data collection

Data collection will begin once ethical approval is given (REB) and will be conducted using the health records of patients hospitalized during the 6 months preceding this approval. Archivists in each center in the study will provide randomly selected lists of the health records of patients meeting inclusion criteria. Data collected on each of the variables under study will be stored in a password-secured file. The complete list of clinical and organizational quality indicators in the scoping review is presented in Appendix 1. The data collection sheet on patients' characteristics and clinical and organizational quality indicators is given in Appendix 2.

3.4.1 Data collection on patients' characteristics

Patients' characteristics refer to certain sociodemographic data such as age, sex and ethnic or cultural origin as well as a patient's clinical profile including stroke diagnosis, type of treatment (thrombolysis IV, thrombectomy), list of medications, presence of a previous stroke, stroke risk factors, comorbidities, severity of stroke (National Institutes of Health Stroke Scale [NIHSS]) and pre-stroke functional independence (modified Rankin score [mRs])

(Gonzalez-Suarez et al., 2018; Langhorne et al., 2018; Mohammed et al., 2020; Muñoz Venturelli et al., 2019; Nathan et al., 2018; Nishimura et al., 2019).

3.4.2 Data collection on clinical and organizational quality indicators

Quality indicators will be measured using the health records of acute stroke patients. Those measured will be classified based on dimensions of performance of care (accessibility of services [accessibility and equity of access], optimization of resources [efficiency and viability] and quality of care [safety, effectiveness, continuity and reactivity]).

3.4.3 Data collection on hospitals' characteristics

Data on hospitals' characteristics will be collected using an environmental analysis method (environmental scan) together with a data collection guide to identify the characteristics of hospitals based on the current clinical documentation and consultations with various clinicians, managers and doctors available. Environmental analysis is used to gather information on events and their relation to the internal and external environment of an organization. The method's main objective is to gather, evaluate and disseminate data for strategic purposes (Clagett, 1987). The data collection guide will be developed using hospital characteristics identified in certain studies retained in the 2024 scoping review (Bélanger et al., 2024) and will be rooted in the conceptual framework Consolidated Framework for Implementation Research (CFIR) to obtain a broad view of the characteristics defining the organizational, contextual and clinical composition of a hospital. The CFIR is a metatheory that allows us to deepen the implementation of innovative interventions within organizations. Its concepts underscore five spheres of influence including, in the present study, 1) characteristics of interventions (e.g., complexity, accessibility), 2) strength and quality of conclusive results), 3) external context (e.g., available resources, guidelines), 4) internal context (e.g., type and number of staff available, structural characteristics) and 5) process (e.g., engagement, planning, execution, reflection). The CFIR takes into account the different actors working with a target clientele and focuses attention on both clinical and organizational contexts and the many complex issues in the field of health (Damschroder et al., 2009). Data will be collected on characteristics including type of center (primary, secondary or tertiary); description of mission and respective role of each center in line with type of designation; geographic distribution; number of persons served by the center; average number of stroke patients admitted each year; number of beds in the stroke care unit; type and number of medical staff available (nurses, nursing assistants, patient care assistants, occupational therapists, physiotherapists, speech therapists, nutritionists, kinesiologists, etc.); presence of multidisciplinary teams (conduct and frequency of meetings); ratio of patients to nurses, nursing assistants, clinicians and patient care assistants; average number of years of experience of nurses

and different clinicians; proportion of nurse technicians and nurse clinicians; number of neurointerventionists, neurovascular specialists, neurologists, internists and general practitioners; protocols and procedures in effect; frequency, type and content of stroke training offered to different medical workers; internal and external resources (material resources, patients' needs, organizational networking, policies, plans or programs in effect, etc.); and methods of communication for transmitting important information to the teams (Gonzalez-Suarez et al., 2018; Langhorne et al., 2018; Muñoz Venturelli et al., 2019; Nishimura et al., 2019). An environmental analysis will be conducted based on observations in the healthcare setting and on consultations with health professionals, different clinicians, doctors and managers available in the different centers. An analysis of protocols, procedures and other documents in effect will also be performed to obtain a detailed picture of each center. First, we will start by collecting needed information from managers and nurse-managers in each establishment by setting up a meeting in advance based on their availability. Second, in the event of missing information, we will arrange with managers to target persons who can supply the missing data. All meetings with clinicians and managers will be scheduled to ensure the availability of the persons concerned. This data collection will serve to paint a portrait of the healthcare centers under study.

3.5 Projected statistical analyses

In response to the first research question, descriptive analyses will be conducted based on measurement of the clinical and organizational quality indicators identified in the acute phase. Medians and interquartile ranges, means and standard deviations and proportions will be used to describe performance of care and services for each center under study and comprehensively for all three centers. Additionally, a contextual description of each center will be presented using data collected on the hospitals' characteristics.

Results of the first objective will highlight indicators that do or do not meet the guidelines for quality of care for persons with ischemic stroke and their caregivers. For indicators presenting extensive data, regression analyses will be performed to identify the determinants likely to influence results regarding these indicators.

Dependent variables are clinical or organizational quality indicators, while independent variables correspond to the sociodemographic characteristics and clinical profile of patients with ischemic stroke. Type of regression analysis will vary consistent with the nature of the dependent variables (dichotomous or continuous) and their distribution (parametric or nonparametric tests).

A univariate regression analysis will first allow us to associate determinants (independent variables) with results for the indicators (dependent variables). Variables with a statistically significant association will then be introduced into a linear or logistic regression model. Additionally, these regression analyses will include

confounding variables that may also influence results from the measurement of clinical and organizational quality indicators. To be statistically significant, results must obtain a value of $p < 0.05$ and have a confidence interval of 95 %. All statistical analyses will be conducted using SPSS 28.0 software. Results will be presented comprehensively for the three centers; they may also be presented individually for the secondary and tertiary centers to see if the associations in them are similar or different. If the number of records in one of these hospitals is not enough for statistical power, the analysis will not be performed.

4. Consent process

This study will be carried out retrospectively by analyzing the health records of patients meeting the admissions criteria. This type of study is more in line with a practice assessment process where the patient's consent is not considered necessary according to the 2018 Tri-Council Policy Statement (TCPS2). However, authorization by the Direction des services professionnels et de la pertinence clinique (DSPPC) following ethical approval of the research is needed to access patients' health records.

5. Project progress

After the ethics certificate and a letter authorizing access to health records have been obtained from the Direction des services professionnels et de la pertinence clinique (DSPPC), the random list of 130 health records of patients admitted within the preceding 6 months can be transmitted to the principal investigator to initiate data collection. Random lists of health records meeting the criteria will be drawn up by an archivist in each of the centers. The data will be collected in all three hospital centers at once based on availability of records.

6. Ethical and regulatory considerations

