	
this sample size is largely sufficient to have a power of 95 %, an alpha set at 0.05 and a minimal effect size of 0.5. The number of patient records retained will provide a sample representative of the hospitalized population in the three hospitals.
 
Finally, a records evaluation test (n=6) will be performed in advance to estimate the time needed to examine each record and allow needed adjustments to be made to conduct research within the context of a doctoral study.

Data collection	
Results measurement:
 
 • Retrospective data collection performed on patients' health records included in the study (patients' sociodemographic and clinical data, results of evaluation of clinical and organizational quality indicators) • Description of hospitals through data collected on their characteristics based on an analysis of the environment and context of the different centers. This data collection will be performed using a structured interview guide (targeted questions) to identify hospitals' characteristics according to the clinical documentation and consultations with various clinicians, managers and doctors available in the centers under study.
Data analysis	
Statistical analyses will be conducted using SPSS software to meet the study's objectives.
 
Objective 1: Retrospective descriptive analysis based on patients' health records
 
Objective 2: Univariate and multivariate analyses; type of analysis based on type of variable (linear and logistical) and according to distribution (parametric and nonparametric tests)

Anticipated impacts	
 • Broaden the state of knowledge regarding acute ischemic stroke by drawing a picture of stroke patient management in three differently designated Quebec hospitals; • Identify the sociodemographic and clinical determinants that may influence the results of certain indicators; • In the long term, this project may contribute to reduce the gap between current practices and guidelines regarding post-acute stroke management; • Optimize acute stroke care and services across Quebec through improved understanding of different hospital contexts.

1. Introduction

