3.3.2 Sample size

Calculation of number of records aims for a certain representativity of the target population at the time of data collection. Given that about 660 patients are hospitalized each year with ischemic stroke in the three centers under study - 400 in the tertiary center, 250 in the secondary center and 12 in the primary center - and the data were collected over a period of 6 months, the sample size is estimated to be some 130 health records, i.e., about 75, 45 and 8 to 10 records respectively. A power calculation in G*Power on analyses of group averages indicates this sample size is largely sufficient to have a power of 95 %, an alpha set at 0.05 and a minimal size effect of 0.5. When the size effect is not known, a minimal size effect of 50 % is acceptable (Julien, 2019). However, a first phase test will be performed with the health records of patients (n =6) hospitalized prior to the date set for the start of data collection to evaluate the average time required to analyze a record. This phase test will be performed on three health records from the secondary center and three from the tertiary center. Finally, this phase will enable needed adjustments to be made regarding implementation of research within the context of a doctoral study. Additionally, the principal investigator will have access to resources to validate the statistical analysis plan for the study duration.

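### The sample is called representative of the three hospitals, but the primary centre is sampled in full and the other two at about 37%, with no weighting stated for pooled results

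*Protocol*

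**What the plan says.** Section 3.3.2 gives the annual volumes as "400 in the tertiary center, 250 in the secondary center and 12 in the primary center", says that "the data were collected over a period of 6 months", and splits the total of some 130 records into "about 75, 45 and 8 to 10 records respectively". Section 5 sets the sampling method: "Random lists of health records meeting the criteria will be drawn up by an archivist in each of the centers". The sample is thus drawn separately by centre.

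Section 3.5 reports the indicators "for each center under study and comprehensively for all three centers". For the regressions it says: "Results will be presented comprehensively for the three centers". It neither plans nor rules out weights for combining the centres.

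The synopsis, under sample size, states: "The number of patient records retained will provide a sample representative of the hospitalized population in the three hospitals". Section 3.3.2 is more cautious and claims only a degree of representativeness. Section 8.1 lists better representation of the stroke population as a strength of using three centres.

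**The concern.** When records are drawn separately in each centre, their total number does not make the pooled sample representative of the three hospitals together. That takes either the same sampling fraction in every centre or weights that restore each centre's share. The Protocol's own figures give unequal fractions, and it states no weights.

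The over-represented centre is the remote one (section 3.1). The Introduction notes that remote hospitals are less likely to have a stroke unit, so its level on some indicators could plausibly differ. A plain pooled proportion, mean or median would then lean towards that centre, while the synopsis tells the reader that it describes the hospitalized population of all three. Section 3.1 justifies the multicentre design by the broad view it gives, and the pooled figures carry that claim.

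**Working it through.** **Inputs (Protocol, section 3.3.2).** Annual admissions are 400, 250 and 12. The window is six months. Planned records are 75, 45 and 8 to 10. Assumption: admissions are even over the year.

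**The plan's own totals.** 400 + 250 + 12 = 662, against the stated figure of about 660. 75 + 45 + 8 to 10 = 128 to 130, against some 130. Both agree.

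**Six-month admissions.** 400/2 = 200, 250/2 = 125 and 12/2 = 6, in total 331.

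**Sampling fractions (records / six-month admissions).**
- Tertiary: 75/200 = 37.5%.
- Secondary: 45/125 = 36.0%.
- Both together: 120/325 = 36.9%.
- Primary: 8 to 10 planned against about 6 expected. The plan asks for more records than it expects to exist, so the centre is taken in full.

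Proportional allocation of 130 records would be 130 × 200/331 = 78.5, 130 × 125/331 = 49.1 and 130 × 6/331 = 2.4.

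**Over-representation of the primary centre.** Records drawn from the window cannot exceed the admissions in it. The consistent cases are therefore 6 of 6, 8 of 8 and 10 of 10, with the other two centres held at 75 of 200 and 45 of 125.

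| Primary records | Share of sample | Share of admissions | Ratio |
|---|---|---|---|
| 6 of 6 | 6/126 = 4.8% | 6/331 = 1.8% | 2.6 |
| 8 of 8 | 8/128 = 6.3% | 8/333 = 2.4% | 2.6 |
| 10 of 10 | 10/130 = 7.7% | 10/335 = 3.0% | 2.6 |

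**Shift in an unweighted pooled proportion.** Shift = (share of sample − share of admissions) × (primary rate − rate elsewhere), taking the tertiary and secondary rates as equal. The share differences are 2.95, 3.85 and 4.71 percentage points.
- 30-point gap: 0.9, 1.2 and 1.4 points.
- 60-point gap: 1.8, 2.3 and 2.8 points.

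Both gaps are illustrations. The Protocol gives no expected indicator values by centre.

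**Sampling error for comparison.** For a pooled proportion of 50% with 130 records, the 95% half-width is 1.96 × √(0.25/130) = 8.6 points, or about 6.7 with a finite population correction.

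**Weights and their cost.** Weight = six-month admissions / records sampled: 200/75 = 2.67, 125/45 = 2.78 and 6/6 = 1. The Kish design effect is n × Σ(N²/n by centre) / (ΣN)².
- 6 of 6: 126 × (533.3 + 347.2 + 6) / 331² = 1.02.
- 10 of 10: 130 × (533.3 + 347.2 + 10) / 335² = 1.03.

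**Records available in the primary centre.** If admissions follow a Poisson distribution with mean 6 (assumption), the chance of at least 8 in the window is 26% and of at least 10 is 8%. The planned 8 to 10 could occur, but it is not what the stated volume leads one to expect.

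**The case against.** The case against has several parts.

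- **Weighting may be set elsewhere.** Section 3.5 is silent on weights, and how strata are combined is often left to a statistical analysis plan, which section 3.3.2 mentions and which is not at hand. This stands: a reader might infer that the plan commits to an unweighted pooled analysis, but the Protocol does not say so. What remains is the synopsis sentence, which attributes representativeness to the number of records. The stated allocation does not deliver that by itself.
- **The size is easily overstated.** Setting 10 planned records against 6 admissions gives 7.7% against 1.8%, or 4.2-fold. The two figures cannot both hold, because 10 records from the window require at least 10 admissions. On consistent counts the factor is about 2.6.
- **Not every pooled figure is affected.** Indicators 3 and 7 are marked as not applicable in a primary care centre, and indicators 5 and 6 concern remote communities rather than patient records. This stands, and the point is limited to patient-level results that apply to all three centres.
- **The effect is small and the per-centre results are sound.** The tertiary and secondary centres are sampled almost proportionally and supply over 92% of the records. Lists are random within each centre, and section 3.1 asks each centre to compare itself with itself. All of this stands.
- **Weighting by volume is one target among several.** Patients move between these centres (section 3.1), so admissions are not distinct patients. That affects what the weighted figure describes. But the synopsis itself names the hospitalized population of the three hospitals as the target, so weighting to volume follows from the Protocol and is not merely a reviewer's preference.

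**Conclusion.** The point holds as a minor one. The synopsis claims a property that a plain pooled figure from this allocation would lack. The primary centre would count about 2.6 times its share of admissions. For an illustrative 30-point gap, pooled patient-level proportions that apply to all centres would move by about 0.9 to 1.4 points (1.8 to 2.8 for 60 points). This is a systematic shift, but it is well below the half-width of about 8.6 points.

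The result rests on even admissions over the year, on 75 and 45 records being reached in the larger centres, and on equal rates in those two centres. A reader might go further and conclude that the sample is unrepresentative in general or that the study's results are biased. The documents do not support that: the imbalance concerns only the mix of centres, within-centre sampling is random, and per-centre results are unaffected.

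**What to change.** 1. In section 3.5, state that pooled descriptive results on patient-level indicators applicable to all three centres weight each record by its centre's actual six-month admissions, taken from the archive count, divided by the records sampled there (about 2.67, 2.78 and 1 if six primary records exist). Compute confidence intervals with a stratified estimator. The weights should not be treated as copies of records, since they sum to about 331 rather than 126.
2. Reword the synopsis sentence to say that pooled figures are weighted to centre volume. If they are left unweighted, say that they describe the sample only.
3. In section 3.3.2, reconcile the 8 to 10 planned primary-centre records with the roughly 6 admissions expected from 12 a year, and adjust the total if needed (75 + 45 + 6 = 126).

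The cost is one weight variable, three archive counts, a few sentences, and about 2% in variance (3% if there are 10 primary records). No extra data collection is needed.

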To ensure equity and quality of care and services at the national level, Canadian and international guidelines are regularly published, disseminated and updated consistent with evolution of the state of knowledge regarding, notably, ischemic stroke. These guidelines are deployed on a continuum of stroke-related care and services involving six phases: 1) public awareness raising, 2) primary prevention, 3) hyperacute management, 4) acute management, 5) rehabilitation, and 6) return and maintenance in the community. This continuum guides the offer of care and services and contributes to optimal follow-up in persons with stroke or at risk of stroke and their caregivers concerning immediate recognition of signs of stroke, rapid restoration of blood flow to the brain with hyperacute revascularization treatments, and organization of care and services based on predefined care trajectories (Ministère de la Santé et des Services Sociaux [MSSS], 2017a). In ischemic stroke, the first aim of treatment is to restore blood flow to the brain as rapidly as possible in order to limit deficits and thus facilitate early rehabilitation supported by caregivers. For a number of years now, the administration of intravenous thrombolysis (IVT) to dissolve blood clots obstructing blood vessels has been the first treatment of choice for persons with ischemic stroke who meet eligibility criteria (Adams et al., 2007; Boulanger et al., 2018; Lindsay et al., 2005). In addition to type of stroke, the main eligibility criterion involves access to the treatment within 4.5 hours from onset of symptoms, which unfortunately restricts its administration (Boulanger et al., 2018; Wardlaw et al., 2014). Studies conducted in Canada report certain issues regarding IVT. Notably, in Québec, in 2016, the Institut national d'excellence en santé et services sociaux (INESSS) revealed that 23 % of all candidates in the province considered eligible for thrombolysis IV had received the treatment (INESSS, 2016). With the advance in treatments since 2015, thrombectomy, which involves removing clots blocking an artery with specialized devices, has become an additional recognized, privileged practice for treating ischemic stroke caused by obstruction of the large vessels (Goyal et al., 2016; Menon et al., 2016; Vidale et Agostoni, 2017). In Quebec, this type of treatment is available in tertiary hospital centers, i.e., specialized centers offering neurointervention. However, according to

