3.1 Type of study

To meet the objectives of the research questions, a retrospective descriptive-correlational study will be conducted based on methods of collecting and analyzing quantitative data. The decision to conduct a retrospective study was made for two reasons: first, the nature of the data collected from records allows us to describe the current state of clinical and organizational practices during the length of patients' stay; and second, this type of study

May 2022

page 11 de 48

[name], [name], [name]

allows for the inclusion of a sample of patients hospitalized during a fixed six-month period. Finally, the feasibility of a retrospective study was considered within the context of a doctoral project with limited resources, time and budget.

In keeping with these considerations, the present study involves a multicentric investigation to take place in three differently designated Quebec hospitals in terms of stroke care. The choice of a multicentric study is based on using a larger sample of patients from different areas to obtain a broad overall view of clinical and organizational practice in stroke management in Quebec. In this study, the primary care center is a multi-vocational center including hospital care that is located in a remote area. The second participating center is a secondary care university hospital that plays an important role in the optimization of stroke care and services throughout its territory given its status as a regional center. The third hospital targeted by the study is a specialized tertiary care center which is nationally recognized for stroke treatment and performs the most thrombectomies in Quebec.

Having different and welldefined missions, these centers maintain an interdependent relation through the offer of proposed care and services. Notably, the patients from the primary care center requiring a thrombectomy are generally transferred to the tertiary center participating in this study to receive treatment. Additionally, although the tertiary care hospital is a thrombectomy center, the patients transferred there must also be returned to the secondary care referral center quickly after treatment to begin rehabilitation as early as possible. Since the majority of guidelines apply in all types of centers irrespective of where the patient is managed, each center must self-compare regarding the achievement of quality indicators.

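### Objective 2 pools the centres and screens patient characteristics without a centre term, so a characteristic that only marks the treating hospital can pass as a determinant

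*Protocol*

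**What the plan says.** **Variables and selection.** Section 3.5 states: "Dependent variables are clinical or organizational quality indicators, while independent variables correspond to the sociodemographic characteristics and clinical profile of patients with ischemic stroke". The first step is univariate: "A univariate regression analysis will first allow us to associate determinants (independent variables) with results for the indicators (dependent variables"). Characteristics that reach significance go on to a linear or logistic model. The same section adds that the regressions will include confounding variables, without naming any.

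**Pooling.** Section 3.5 commits to results for the three centres together. Results for the secondary and tertiary centres separately are permitted, not required, and are dropped if a hospital has too few records for statistical power.

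**Centre and case mix.** On thrombectomy, the Introduction says: "In Quebec, this type of treatment is available in tertiary hospital centers, i.e., specialized centers offering neurointervention". Section 3.1 adds that "the patients from the primary care center requiring a thrombectomy are generally transferred to the tertiary center participating in this study to receive treatment". It also says that patients treated at the tertiary centre are sent back to the secondary centre soon afterwards, and that each centre should be compared with itself. Section 3.4.1 counts type of treatment, including thrombectomy, as part of the patient's clinical profile.

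**Centre and practice.** The Introduction cites studies in which hospital profile and level of care processes affected results. Hypothesis 2 allows gaps from guidelines to differ by type of centre, and hypothesis 4 allows the determinants to differ as well.

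**Data.** Centre is recorded for each patient as item B1 in Appendix 2, under sociodemographic characteristics.

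**The concern.** A variable linked both to a patient characteristic and to the indicator confounds their association. The protocol gives its own reasons to expect centre to be such a variable: referral shapes who is treated where, and practice may differ by type of hospital. A univariate screen has no centre term by construction, so it credits part of any between-centre difference in an indicator to whichever characteristics are distributed unevenly across centres. Treatment type, home region (B5) and distance (B6) are obvious candidates; severity is a likely one.

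Listing B1 among the sociodemographic items does not settle this. As one more candidate, centre would stay only if it passed the screen, and the other characteristics would already have been selected without it.

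At stake is the answer to research question 2. Section 8 intends the identified determinants to inform an intervention model adapted to patients' needs. A hospital difference read as a patient trait would misdirect that work. The unadjusted screen can also err the other way and discard a real determinant that centre masks.

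**Working it through.** **Inputs from the protocol.** Planned records (section 3.3.2): "i.e., about 75, 45 and 8 to 10 records respectively", in the order tertiary, secondary, primary. These add to 75 + 45 + 8 = 128 up to 75 + 45 + 10 = 130, which agrees with the stated total of about 130. Significance level: 0.05. The plan gives no figure for the effect of centre, so there is none to reproduce, and the power statement in section 3.3.2 does not bear on this point.

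**Assumed inputs.** The documents give neither case mix nor indicator rates by centre. All the percentages below are assumptions. In every scenario the characteristic has no association with the indicator inside either centre (true odds ratio 1).

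**Formula.** For a centre with n records, indicator achievement p and characteristic prevalence q, the expected cells are nqp (characteristic, achieved), nq(1−p) (characteristic, not achieved), n(1−q)p and n(1−q)(1−p). Add the cells over the two centres to get a, b, c, d. The pooled odds ratio is ad/(bc).

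**Worked example (moderate gaps): achievement 80% vs 50%, prevalence 60% vs 30%.**
- a = 75×0.6×0.8 + 45×0.3×0.5 = 36 + 6.75 = 42.75
- b = 75×0.6×0.2 + 45×0.3×0.5 = 9 + 6.75 = 15.75
- c = 75×0.4×0.8 + 45×0.7×0.5 = 24 + 15.75 = 39.75
- d = 75×0.4×0.2 + 45×0.7×0.5 = 6 + 15.75 = 21.75
- Pooled odds ratio = (42.75×21.75)/(15.75×39.75) = 1.49

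**False significance.** For each scenario, 20,000 samples were simulated. The pooled table was tested by uncorrected chi-square at 0.05, which stands for the univariate screen. A Mantel-Haenszel test stratified by centre stands for holding centre fixed.

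| Scenario (tertiary vs secondary) | Achievement | Prevalence | Pooled OR | Screen without centre | Centre held fixed |
|---|---|---|---|---|---|
| Mild gaps | 70% vs 60% | 60% vs 30% | 1.13 | 6% | 5% |
| Moderate gaps | 80% vs 50% | 60% vs 30% | 1.49 | 17% | 5% |
| Large gaps | 85% vs 45% | 60% vs 20% | 2.11 | 44% | 5% |
| Equal prevalence | 80% vs 50% | 45% vs 45% | 1.00 | 5% | 5% |
| Equal achievement | 65% vs 65% | 60% vs 30% | 1.00 | 5% | 5% |

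The last two rows confirm the mechanism: both links to centre must be present.

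**Check with the primary centre included.** Logistic models on 75, 45 and 9 records, 2,000 samples, likelihood-ratio test:
- Prevalence 30/10/0% with achievement 70/50/40%: falsely significant in 11.6% without centre and 5.6% with it.
- Prevalence 50/10/0% with achievement 80/50/30%: 44.6% without centre and 5.3% with it.

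**The case against.** **Confounders are promised.** Section 3.5 says the regressions will include confounding variables, and which ones is detail that a statistical analysis plan often supplies. This stands in part. If centre is among them, the final estimates are protected, as the 5% column shows. But the sentence neither names nor excludes centre, and the selection step stays unadjusted in any case.

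**By-centre results are foreseen.** They would be a genuine within-centre check, but they are optional and conditional on numbers.

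**The size is assumed.** This is correct. With mild gaps the excess is about one percentage point. The percentages describe the univariate step, not the multivariable model.

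**Adjustment is not neutral.** Where a patient lives helps decide which hospital treats them, so for home region and distance centre may lie on the pathway to care, and adjusting could remove a real access effect. This stands. It calls for showing both estimates, not for leaving centre out.

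**The aims are modest.** Section 8.2 says the associations will not explain cause. It still presents them as elements likely to influence the results.

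**A stronger reading to avoid.** Because thrombectomy is performed at the tertiary level, a reader might infer that it cannot be separated from the tertiary hospital and should be analysed there only. Section 3.1 does not support this: treated patients return to the secondary centre, and item C3 records whether thrombectomy was given, not where. Secondary records can therefore show it. With achievement 80% vs 50% and thrombectomy in 40% of tertiary records, an assumed 10%, 20% or 30% among secondary records gives pooled odds ratios of 1.65, 1.36 and 1.15, and false significance of 19%, 10% and 6%. Thrombectomy is a likely marker of centre, not a synonym for it.

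**Conclusion.** The concern holds in a limited form. Section 3.5 commits to a pooled analysis whose selection step ignores centre, and nothing in the protocol commits the final model to include it. A characteristic unrelated to the indicator inside every centre can pass the screen, and can be reported as a determinant if centre is missing from the final model.

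The illustrated false-significance rate at the screen runs from about 6% to 44%, against 5% with centre held fixed. The range rests on assumed achievement and prevalence by centre, on 75 and 45 records, and on no within-centre association. Without a centre difference in both the characteristic and the indicator, there is no bias. A reader might infer that the reported determinants will be wrong; the documents do not support that, since centre may yet be one of the unnamed confounders and the actual gaps are unknown.

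**What to change.** In section 3.5:

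1. State that centre (B1) is kept as a fixed term in every pooled Objective 2 model, at the screening step and in the multivariable model, whatever its significance.
2. Fit these models on the tertiary and secondary records, and describe the primary centre only. It has 8 to 10 planned records, and its stated 12 admissions a year imply about 12/2 = 6 in six months.
3. State that the estimates are associations within centre.
4. For home region and distance (B5, B6), also show the estimate without centre, with a note that centre may lie on the pathway to care.

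The cost is a change of wording, one degree of freedom per model, and slightly wider intervals for characteristics that track centre. The primary centre's few records leave the regressions but stay in the description. Centre is already collected, so no new data are needed.
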